4.5.2. Secondary Efficacy Variable(s)

Virologic

- Time-weighted average change from baseline in viral load at each timepoint, as measured by RT-qPCR in NP samples
- Change from baseline in viral load at each timepoint through day 7, as measured by RT-qPCR in NP samples
- Proportion of patients with viral loads below the limit of detection at each visit

4.5.3. Exploratory Efficacy Variable(s)

Virologic

- Change from baseline in viral load through day 29 as measured by RT-qPCR in NP swab samples

Clinical

- Proportion of patients with COVID-19-related medically attended visits (MAVs) or all-cause mortality through day 29 and day 169

Note: A COVID-19-related medically-attended visit will be defined as follows: hospitalization, emergency room (ER) visit, urgent care visit, physician's office visit, or telemedicine visit, with the primary reason for the visit being COVID-19. Refer to Section 9.2.9 of the Protocol Amendment 1 for more information.

Drug Concentration

- Concentrations of REGN14256, casirivimab and imdevimab in serum over time

4.6. Safety Variables

4.6.1. Adverse Events and Serious Adverse Events

An adverse event (AE) is any untoward medical occurrence in a patient administered a study drug which may or may not have a causal relationship with the study drug. All adverse events are to be coded to a “Preferred Term” and associated primary “System Organ Class (SOC)” according to the latest available version of Medical Dictionary for Regulatory Activities (MedDRA®).

Treatment-emergent adverse events are defined as the AEs that are not present at baseline or represent the exacerbation of a pre-existing condition during the on-treatment period. A Serious Adverse Event is an AE that is classified as serious according to the criteria specified in Section 10.2.2 of the Protocol Amendment 1. All TEAEs and SAEs will be collected through the end of study.

4.6.2. Adverse Events of Special Interest

An AESI (serious or non-serious) is one of scientific and medical interest specific to the Sponsor’s product or program, for which ongoing monitoring and rapid communication by the investigator to the Sponsor can be appropriate. Adverse events of special interest for this study include the following:

- Grade ≥ 3 injection-site reactions (ISRs) through study day 4
- Grade ≥ 3 hypersensitivity reactions through study day 29

All the adverse events define above in Section 4.6.1 and Section 4.6.2 must be reported with investigator’s assessment of the event’s seriousness, severity, and causality to the blinded study drug.

The severity of adverse events (including test findings classified as AEs) will be graded using the current version of the NCI-CTCAE v5.0. Treatment-emergent AEs, SAEs, or AESIs not listed in the NCI-CTCAE will be graded according to the scale in Table 6 of the Protocol Amendment 1. The grading systems for anaphylaxis, allergic reaction (hypersensitivity), and injection-site reaction are provided in Table 7 of the Protocol Amendment 1.

The investigator must provide causality assessment as whether there is a reasonable possibility that the drug caused the adverse event, based on evidence or facts, his/her clinical judgment, and the following definitions. For more information regarding the causality assessment, refer to Section 10.2.5 of the Protocol Amendment 1.

Laboratory results, vital signs, and other diagnostic results or findings (e.g., positive pregnancy test) should be appraised by the Investigator to determine their clinical significance. Isolated abnormal laboratory results, vital sign findings, or other diagnostic findings (i.e., not part of a reported diagnosis) should be reported as AEs if they are symptomatic, require corrective

treatment, or constitute an AE in the investigator's clinical judgement. More details on the reporting of adverse events can be found in Section 10.1.1 of the Protocol Amendment 1.

4.6.3. Laboratory Safety Variables

Hematology, chemistry, and serum β -HCG pregnancy testing samples will be analyzed by a central laboratory. The laboratory tests listed below will only be performed based on samples that are collected according to the corresponding Schedules of Events (Section 10.1). Tests will include:

Blood Chemistry

Sodium	Total protein, serum	Total bilirubin
Potassium	Creatinine	Total cholesterol
Chloride	Blood urea nitrogen (BUN)	Triglycerides
Carbon dioxide	Aspartate aminotransferase (AST)	Uric acid
Calcium	Alanine aminotransferase (ALT)	Creatine phosphokinase (CPK)
Glucose	Alkaline phosphatase	
Albumin	Lactate dehydrogenase (LDH)	

Hematology

Hemoglobin	Differential:
Hematocrit	Neutrophils
Red blood cells (RBCs)	Lymphocytes
White blood cells (WBCs)	Monocytes
Red cell indices	Basophils
Platelet count	Eosinophils

Other Test(s)

β -HCG pregnancy testing (serum)

4.6.4. Vital Signs

The following vital signs parameters will be recorded at multiple time points according to Schedule of Time and Event Table (Section 10.1):

- Respiratory rate (bpm)
- Heart rate (bpm)
- Systolic and diastolic blood pressures (mmHg)
- SpO₂ (%)
- Body temperature (°C)

4.7. Pharmacokinetic Variables

The PK variables are the concentrations of REGN14256, casirivimab and imdevimab in serum at each timepoint. These sampling timepoints are specified in the corresponding Schedule of Events (Section 10.1).

4.8. Exploratory Variables

Exploratory variables include, but not limited to, the patient-reported COVID-19 symptoms and outcomes assessed by electronic questionnaires (e.g., SE-C19), the exploratory parameters (e.g., physical activities) measured using wearable devices, and the parameters collected from viral sequencing tests, viral infectivity assays, serological immunoassays for Anti-SARS-CoV-2 Antibodies, and serum and plasma samples for exploratory research. Refer to section 9.2.8 of the Protocol Amendment 1 for more information. These results may be reported outside of the clinical study report (CSR).

5. STATISTICAL METHODS

For continuous variables, descriptive statistics will include the following: the number of patients reflected in the calculation (n), mean, median, standard deviation, minimum, and maximum.

For categorical or ordinal data, frequencies and percentages will be displayed for each category.

5.1. Demographics and Baseline Characteristics

Demographic and baseline characteristics will be summarized descriptively by treatment group, and by all groups combined using FAS, mFAS, and SAF. The corresponding subgroup summaries by baseline anti-SARS-CoV-2 serostatus will also be provided.

5.2. Medical History

Medical history will be summarized by primary SOC and PT by treatment group and all groups combined using SAF. The table will be sorted by decreasing frequency of SOC followed by PT based on the overall incidence across treated groups.

5.3. Prior/concomitant Medications and Procedures

Prior or concomitant medications/procedures will be summarized by treatment groups using SAF. Summaries will present patient counts (and percentages) for all medications, dictionary coded by WHODRUG, by decreasing frequency of the overall group incidence (or high dose group incidence in tables where the overall is not presented) of ATC followed by ATC level 2, ATC level 4 and preferred term.

5.4. Prohibited Medications

Prohibited medications will be summarized using SAF in a similar way as described above for concomitant medications.

5.5. Subject Disposition

The following summaries will be provided using FAS:

- The total number of screened patients/subjects who have signed ICF
- The total number of randomized patients: received a randomization number
- The total number of screening phase discontinuation, and the reasons for discontinuation
- The total number of patients randomized, patients randomized and treated, patients randomized but not treated, and patients treated but not randomized
- The total number of patients who discontinued the study, and the reasons for discontinuation
- A summary of analysis sets including FAS, mFAS, SAF, and PKAS.

5.6. Extent of Study Treatment Exposure and Compliance

5.6.1. Measurement of Compliance

Treatment compliance is not applicable for this study since the study drug is administered once at the site.

5.6.2. Exposure to Investigational Product

Exposure to study drug will be examined for each patient as recorded on the Drug Administration - Injection CRF. The following variables will be analyzed by treatment group based on the SAF population:

- Duration of injection
- Total volume of drug administered (units: mL)
- Number of patients with total planned dose administered (yes/no)
- Number of patients with injection interruptions

The number and percentage of patients randomized and exposed to double-blind study drug will be presented for each treatment group.

5.7. Analyses of Efficacy Variables

5.7.1. Analysis of Primary Efficacy Variable(s)

Virology

The primary virologic efficacy variable is time-weighted average (TWA) change from baseline in viral load from day 1 to day 7, as measured by RT-qPCR in NP swab samples. The primary virologic efficacy variable will be analyzed descriptively by treatment group, and by all groups combined in the mFAS population. The corresponding subgroup analyses by baseline anti-SARS-CoV-2 serostatus will also be performed.

The analyses will be based on the observed data with no imputation for missing data except the following cases: uncertain viral load values with less than the lower limit of quantification of the PCR assay but with positive qualitative results are imputed with half of lower limit of quantification of the PCR assay; uncertain values with negative RNA are imputed with 0 log₁₀ copies/mL if the reason for the uncertain values is not a failed test. The primary efficacy variable will be calculated using trapezoidal rule, i.e., area under the curve for change from baseline at each time point from day 1 to last observation divided by the number of days from day 1 to day of last observation.

5.7.2. Analysis of Secondary Efficacy Variables

Virology

Time-weighted average change from baseline in viral load at each timepoint, as measured by RT-qPCR in NP samples, will be analyzed descriptively in a similar way as described above for the primary virologic efficacy variable.

To assess the time course of treatment effect in viral load, change from baseline in viral load at each timepoint through day 7, as measured by RT-qPCR in NP samples, will be analyzed descriptively in the mFAS population. The viral load at each visit up to day 7 along with the change from baseline in viral load (log10 copies/mL) will be summarized by treatment group with descriptive statistics. The line plot of mean (+/-se) viral load change from baseline in log10 scale at each visit and the line plot of mean (+/-se) viral load in log10 scale at each visit will also be presented.

Proportion of patients with viral loads below the limit of detection at each visit through day 29 will be presented by treatment group. The percentage at each visit is derived using the number of patients with NP swab samples at the visit as the denominator.

The corresponding subgroup analyses/graphs by baseline anti-SARS-CoV-2 serostatus will be performed for all the secondary virologic efficacy analyses.

5.7.3. Analysis of Exploratory Variables

Virology

The analysis of change from baseline in viral load through day 29, as measured by RT-qPCR in NP swab samples, will be conducted referring to the previously detailed analysis of change from baseline in viral load at each timepoint through day 7.

Clinical Outcomes

The proportions of patients with medically attended visits (MAVs) due to COVID-19 or all-cause death through Day 29 and Day 169 will be summarized with descriptive statistics. The analyses will be performed based on the observed data from the mFAS patients. Listings of COVID-19-related MAVs during the study will also be summarized and presented.

5.7.4. Adjustment for Multiple Comparison

There is no issue with multiplicity for the primary efficacy variable.

5.8. Analysis of Safety Data

The analysis of safety and tolerance will be performed on the SAF, as defined in Section 3.2.

The safety analysis will be based on the reported AEs and other safety information (clinical laboratory evaluations and vital signs).

Thresholds for Potential Clinically Significant Values (PCSV) in laboratory variables and vital signs are defined in Section [10.2](#).

The summary of safety results will be presented for each treatment group.

5.8.1. Adverse Events

Definitions

For safety variables, 2 periods are defined:

- The pretreatment period is defined as the time from signing the ICF to before study drug administration.

- The observation period is defined as the time of study drug administration to the last study visit. Treatment-emergent adverse events are defined as those that are not present at baseline or represent the exacerbation of a pre-existing condition during the on-treatment period.

Analysis

All AEs reported in this study will be coded using the Medical Dictionary for Regulatory Activities (MedDRA®).

Summaries of TEAEs by treatment group will include:

- The number (n) and percentage (%) of patients with at least 1 TEAE through day 29 and day 169 by SOC and PT
- TEAEs by severity (according to the grading scale outlined in Section 10.2.4 of the Protocol Amendment 1), presented by SOC and PT
- The number (n) and percentage (%) of patients with at least 1 TEAE related to study treatment through day 29 and day 169 by SOC and PT

Summaries of SAEs and AESIs by treatment group will include:

- The number (n) and percentage (%) of patients with at least 1 treatment-emergent SAE through day 169 by SOC, PT, and severity
- The number (n) and percentage (%) of patients with at least 1 treatment-emergent SAE through day 169 by SOC, PT, and relationship to study drug
- The number (n) and percentage (%) of patients with at least 1 AESI through day 29 (defined with a PT or a prespecified grouping)

Listings of deaths, SAEs, AESIs, and TEAEs leading to study discontinuation will be summarized and presented by treatment group.

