4. ENDPOINTS

4.1. Primary Endpoints

4.1.1. Phase 1 (Safety and Tolerability)

The primary safety endpoints of phase 1 are:

- TEAEs and severity of TEAEs through day 29
- Proportion of patients with ISRs and severity of ISRs throughout the study
- Proportion of patients with hypersensitivity reactions and severity of hypersensitivity reactions over time

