8.5.2. Local Injection-Site Reactions

Local injection-site reactions must be reported as AEs and graded according to Section 10.2.4.

Injection-site reactions occurring through day 4 are considered AESIs and require expedited reporting to the Sponsor (Section 10.1.2).

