10.2.4. Severity

The severity of adverse events (including test findings classified as AEs) will be graded using the current version of the NCI-CTCAE v5.0.

Treatment-emergent AEs, SAEs, or AESIs not listed in the NCI-CTCAE will be graded according to the scale in [Table 6](#). The grading systems for anaphylaxis, allergic reaction (hypersensitivity), and injection-site reaction are provided in [Table 7](#)

Table 6: NCI-CTCAE (v5.0) Severity Grading System for Adverse Events: General Guideline

Grade	Severity	Description
1	Mild	Asymptomatic or mild symptoms; clinical or diagnostic observations only; intervention not indicated
2	Moderate	Minimal, local, or noninvasive intervention indicated; limiting age appropriate instrumental activities of daily living (ADL) ¹
3	Severe	Severe or medically significant but not immediately life threatening; hospitalization or prolongation of hospitalization indicated; disabling; limiting self-care ADL ²
4	Life-threatening	Life threatening consequences; urgent intervention indicated
5	Death	Death related to adverse events

¹ Instrumental ADL refers to preparing meals, shopping for groceries or clothes, using the telephone, managing money, etc.

² Self-care ADL refers to bathing, dressing, and undressing, feeding self, using the toilet, taking medications, and not bedridden.

Table 7: NCI-CTCAE (v5.0) Severity Grading System for Anaphylaxis, Allergic Reactions and Injection-Site Reactions

Grade	CTCAE Term		
	Anaphylaxis ¹	Allergic Reaction (hypersensitivity) ²	Injection-Site Reaction ³
1	N/A	Systemic intervention not indicated	Tenderness with or without associated symptoms (eg, warmth, erythema, itching)
2	N/A	Oral intervention indicated	Pain; lipodystrophy; edema; phlebitis
3	Symptomatic bronchospasm, with or without urticaria; parenteral intervention indicated; allergy-related edema/angioedema; hypotension	Bronchospasm; hospitalization indicated for clinical sequelae; intravenous intervention indicated	Ulceration or necrosis; severe tissue damage; operative intervention indicated

4	Life-threatening consequences; urgent intervention indicated	Life-threatening consequences; urgent intervention indicated	Life-threatening consequences; urgent intervention indicated
5	Death	Death	Death

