11.1. Statistical Hypothesis

Phase 1

No formal hypothesis testing is planned for phase 1. The safety and tolerability objectives will be evaluated by estimating the proportion of patients with TEAEs and SAEs through day 29 and AESIs, which will include ISRs (grade ≥ 3) through day 4 and hypersensitivity reactions (grade ≥ 3) through day 29.

Phase 1/2

There are two null hypotheses to be tested in phase 1/2 (ie, based on data from phase 1 and phase 2):

- **H_{a1}**: There is no treatment difference between REGN14256 in combination with imdevimab compared to placebo in terms of time weighted average daily change from baseline in viral load (\log_{10} copies/mL) from day 1 to day 7 for the seronegative patients.
- **H_{a2}**: There is no treatment difference between REGN14256 alone compared to placebo in terms of time weighted average daily change from baseline in viral load (\log_{10} copies/mL) from day 1 to day 7 for the seronegative patients.

Phase 1/2/3

The primary null hypothesis to be tested in phase 1/2/3 (ie, based on data from phase 1, phase 2, and phase 3) is:

- **H_{b1}**: There is no difference in time to COVID-19 symptoms resolution for REGN14256 in combination with imdevimab compared to placebo for the seronegative patients.

A hierarchical testing procedure will be applied to control for multiplicity and to maintain the study-wise type I error rate at two-sided 0.05 level.

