1.2. Study Objectives

1.2.1. Primary Objectives

The primary objectives of the phase 1 are to:

- Evaluate the safety and tolerability of REGN14256+imdevimab and REGN14256 monotherapy, as measured by treatment-emergent adverse events (TEAEs), injection-site reactions (ISRs), and hypersensitivity reactions
- Evaluate the virologic efficacy of REGN14256+imdevimab and REGN14256 monotherapy compared to placebo, as measured by time-weighted average (TWA) change from baseline in viral load through day 7
- Evaluate the clinical efficacy of REGN14256+imdevimab compared to placebo, as measured by COVID-19 symptoms resolution

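### Any-grade injection-site and hypersensitivity reactions are phase 1 primary endpoints, but the only analysis dedicated to them is of grade ≥3 events over shorter windows

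*SAP*

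**What the plan says.** Protocol 4.1.1 lists three phase 1 primary safety endpoints. The first is TEAEs and their severity through day 29. The other two are "Proportion of patients with ISRs and severity of ISRs throughout the study" and "Proportion of patients with hypersensitivity reactions and severity of hypersensitivity reactions over time". Neither of these has a grade floor. SAP 1.2.1 keeps them in the primary safety objective: safety and tolerability "as measured by treatment-emergent adverse events (TEAEs), injection-site reactions (ISRs), and hypersensitivity reactions".

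The analysis text is narrower. Protocol 11.1 evaluates the phase 1 safety objective by the proportion of patients with "TEAEs and SAEs through day 29 and AESIs, which will include ISRs", and there both ISRs and hypersensitivity reactions are restricted to grade ≥3. Protocol 11.4.5.1 gives each class its own line, again at grade ≥3, to day 4 and day 29. SAP 4.6.2 defines the AESIs in the same way, the first being grade ≥3 "injection-site reactions (ISRs) through study day 4". SAP 5.8.1 merges the two classes into one line, "patients with at least 1 AESI through day 29 (defined with a PT or a prespecified grouping"), and does not say what the grouping is.

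SAP 5.8.1 also has general tables with no grade floor: TEAEs by system organ class (SOC) and PT through day 29 and day 169, TEAEs by severity, and treatment-related TEAEs. Low-grade reactions feed into these. Protocol 8.5.2 states: "Local injection-site reactions must be reported as AEs and graded". Protocol 8.5.1 says the same of systemic injection reactions.

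**The concern.** A primary endpoint should have an analysis that estimates it. Here the endpoint is a proportion of patients with any reaction and its severity, while the table dedicated to the class answers a different question: how many patients had a severe reaction early on. For ISRs the two are far apart. Protocol Table 7 describes grade 3 as "Ulceration or necrosis; severe tissue damage; operative intervention indicated", whereas tenderness, erythema, pain and edema are grades 1 and 2. Those are the reactions that describe the local tolerability of four subcutaneous injections.

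SAP section 1 says enrollment stopped during phase 1 and that phases 2 and 3 never opened. No later phase can supply these estimates. SAP 1.2.4 explains that inferential analyses are dropped and that endpoints will be described, but it does not say that two primary endpoints are reduced to grade ≥3.

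**Working it through.** **1. Endpoint against analysis.**

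| | Endpoint (Protocol 4.1.1) | Dedicated line (SAP 5.8.1 with 4.6.2) |
|---|---|---|
| ISR, grade | any | ≥3 |
| ISR, window | throughout the study (day 169) | to day 4 |
| Hypersensitivity, grade | any | ≥3 |
| Hypersensitivity, window | over time | to day 29 |
| Summary | proportion and severity, each class | n (%) with any AESI, classes not separated |

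**2. Can the general TEAE tables stand in?** They hold the right events, but not necessarily the right count. One patient may have several PTs, and hypersensitivity PTs can fall under several SOCs. Take a hypothetical arm of 20 with three ISR rows of 3, 3 and 2 patients. The number with any ISR is at least the largest row, 3, and at most the sum, 3 + 3 + 2 = 8. The proportion could lie anywhere from 3/20 = 15% to 8/20 = 40%. The severity table is also by SOC and PT, so it does not state each patient's maximum grade over the class.

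**3. What the grade ≥3 line can show.** Planned size (Protocol 3.2.1.2): about 100 patients in 5 arms, 100/5 = 20 per arm, which agrees with the protocol's figure. The final number is not stated. Neither document gives an event rate; Protocol 3.3 says only that the risk is expected to be low. The rates below are therefore assumptions.

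P(no event among n) = (1 − p)^n:

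| Assumed true rate p | n = 20 (one arm) | n = 100 (all planned) |
|---|---|---|
| 0.1% | 0.98 | 0.90 |
| 0.5% | 0.90 | 0.61 |
| 1% | 0.82 | 0.37 |
| 2% | 0.67 | 0.13 |
| 5% | 0.36 | 0.01 |

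For example, 0.99^20 = 0.82 and 0.95^20 = 0.36. A zero in one arm has probability of at least 0.95 only if p is about 0.25% or less (0.9975^20 = 0.95).

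Exact two-sided 95% upper limit after 0 of n is 1 − 0.025^(1/n). For n = 20, 1 − 0.025^(1/20) = 16.8%.

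**4. What an any-grade line would show.** At assumed any-grade rates of 5%, 10% and 20%, P(0 of 20) = 0.36, 0.12 and 0.01. Precision is modest: an illustrative 4/20 gives 20%, exact 95% CI 5.7% to 43.7%. That is still an estimate of the endpoint, which the grade ≥3 count is not.

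**The case against.** The strongest reply is that nothing is lost. A reader might infer from the AESI line that two primary endpoints have no analysis, or that the primary safety question will be answered with near-certain zeros. The documents support neither inference. All injection reactions are reported and graded as AEs, and SAP 5.8.1 tabulates TEAEs of every grade by arm through day 29 and day 169, by severity and by relatedness. TEAEs are themselves a phase 1 primary endpoint, so primary safety does not rest on the AESI line. How likely a zero is depends on a rate that nobody has stated.

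Scatter over PTs is also possible rather than certain. Protocol 10.1.1 asks for the diagnosis as the AE term, and Table 7 grades injection-site reaction and allergic reaction as single terms. If sites report that way, one row could come close to the ISR endpoint. Finally, the narrowing begins in Protocol 11.1 and 11.4.5.1, and the SAP follows them.

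All of this stands, and it limits the point. It does not remove it. Whether the PT rows yield the endpoint is left to reporting and coding practice, less reliably for hypersensitivity than for ISRs. With no grouping fixed in advance, the choice of qualifying PTs stays open. Rash shows the difficulty: it is an item on the SE-C19 COVID-19 symptom instrument and could also be reported as a reaction to study drug.

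**Conclusion.** The point holds as a mismatch between endpoint and analysis. Two of the three phase 1 primary safety endpoints have no prespecified any-grade, patient-level summary and no defined MedDRA grouping, and their only dedicated line is grade ≥3 over shorter windows. The underlying events are collected, graded and tabulated at PT level, so the gap can be closed fully.

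On size: at 20 patients per arm, an empty grade ≥3 cell is likely if the true rate is around 1% or below (probability 0.82 or more), and such a cell excludes only rates above 16.8%. This rests on the planned 20 per arm and on assumed rates. An arm that enrolled fewer than 20 would show zeros more often and have a higher upper limit.

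A related inconsistency affects the same line. Protocol 8.5.1 and 8.5.2 describe systemic reactions through day 29 and ISRs through day 4 as AESIs with no grade floor, whereas Protocol 10.1.3 and SAP 4.6.2 require grade ≥3. What the AESI line contains depends on which reading is applied.

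**What to change.** In SAP 5.8.1 add two primary safety tables by treatment group:

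- n (%) of patients with at least one ISR of any grade;
- n (%) of patients with at least one hypersensitivity reaction of any grade.

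Count each patient once, at maximum grade, through day 29 and through day 169. Write the MedDRA grouping for each class into the SAP before unblinding; SAP section 1 allows revisions until the blind is broken. Keep the grade ≥3 AESI table as a supplement. Exact 95% confidence intervals are optional, since the plan is descriptive.

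No pooled column over the REGN14256 arms is needed. The objectives name the combination and the monotherapy separately. At 300 mg per active injection, the monotherapy arm receives 600/300 = 2 active injections and the combination arm 1200/300 = 4, so pooling would blur local tolerability.

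Align Protocol 11.1 with 4.1.1; if the protocol is not amended again, SAP 1.2.4 is the natural place to record the change. Reconcile Protocol 8.5.1 and 8.5.2 with Protocol 10.1.3 and SAP 4.6.2 on the grade floor for AESIs.

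The cost is some SAP wording and a little extra programming, with no new data.
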